## 6.1.2 DLT

### 6.1.2.1 Definition of DLT

DLTs are defined as treatment-related AEs that occur within the first 28 days of treatment and that meet one of the criteria described below based on CTCAE Version 4.03 (issued June 14, 2010) [13].

1. Grade 3 or higher toxicity

Clinical laboratory abnormalities meet this criterion if they are found at 2 consecutive time points 7 or more days apart, except for ALT or AST  $> 3 \times$  upper limit of normal (ULN), total bilirubin  $> 2 \times$  ULN, or prothrombin time-international normalized ratio (PT-INR)  $> 1.5$  at 2 time points 2 or more days apart.

2. Either of the following ECG findings at 2 time points 7 or more days apart

- QT/Fridericia corrected QT (QTcF)  $> 500$  msec after treatment initiation
- QT/QTcF interval prolongation  $> 60$  msec postdose

The QTcF interval will be calculated using Fridericia's equation (QT/RR0.33).

If it is difficult to determine whether or not an event is a DLT and the subject who experienced the event should be included in the DLT analysis set, the sponsor will consult the SMC before making a final decision on whether or not the event is a DLT.

Study treatment will be continued until the end of the 28-day treatment period unless a DLT occurs. If a subject is withdrawn from the study for a reason other than a DLT or if treatment compliance is below 80% (23 doses), the subject will be considered ineligible for inclusion in the DLT analysis set, and replacement subjects will be added in order to obtain 3 or 6 evaluable subjects.

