  - b. Patients with uncontrolled hypertension (systolic blood pressure > 150 mmHg and diastolic blood pressure > 90 mmHg at 2 separate measurements taken no more than 60 minutes apart at screening). Patients whose blood pressure is brought under control by antihypertensive medication may be rescreened.
  - c. Patients with myocardial infarction, unstable symptomatic ischemic heart disease, arrhythmias of CTCAE Grade > 2, thromboembolism (deep vein thrombosis, pulmonary embolism, or symptomatic cerebrovascular events), or other heart diseases (eg, pericardial effusion, restrictive cardiomyopathy). However, chronic stable atrial fibrillation controlled by stable anticoagulant therapy will be allowed.
13. Patients with bilateral hydronephrosis or bladder neck outlet obstruction.
  14. Known hypersensitivity to TAK-385, TAK-385 excipients, or GnRH antagonists.
  15. Patients with a past history of gastrointestinal tract treatments (including gastrectomy) or gastrointestinal disease that could affect the drug absorption or tolerability (malabsorption, esophageal reflux, peptic ulcer, erosive esophagitis).
  16. Patients positive for hepatitis B surface antigens (HBsAg), hepatitis C virus (HCV) antibodies, human immunodeficiency virus (HIV) antibodies, or serologic test for syphilis, or with life-threatening disease other than cancer, at screening.
  17. Clinically relevant ECG abnormalities, or the following ECG abnormalities, at screening.
    - a. Q-wave infarction, unless identified 6 or more months prior to TAK-385 treatment initiation
    - b. QTcF interval > 450 msec (when calculating the QTc interval, Fridericia's equation  $[QT/RR^{0.33}]$  will be used)
  18. Patients with congenital QT prolongation.
  19. Current use of Class 1A or Class 3 antiarrhythmic medications.
  20. New York Heart Association [18] Class III or IV heart failure ([Appendix H](#)).
  21. Patients with clinical laboratory abnormalities suggesting clinically relevant underlying disease, or with any of the following abnormal results, at screening.
    - Serum creatinine  $\geq 2.0$  mg/dL
    - ALT or AST  $\geq 1.5 \times$  ULN for the investigational site
    - Total bilirubin  $\geq 2 \times$  ULN for the investigational site
    - Neutrophil count < 1,500/mm^3, platelet count < 100,000/ $\mu$ L, hemoglobin < 10.0 g/dL

- Results of heart-related tests (creatine kinase MB [CK-MB] and cardiac troponin T) exceeding the investigational sites reference value.

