5.3.2 Vital Signs, Physical Findings, and Other Observations Related to Safety

5.3.2.1 Vital Signs and Weight

Analysis Set: Safety Analysis Set Analysis

Variable(s) :	Body Temperature (C)		
	Systolic Blood Pressure (mmHg)		
	Diastolic Blood Pressure (mmHg)		
	Pulse (bpm)		
	Weight (kg)		
Visit:	(1) and (2): Baseline, D7, D14, D21, D28, SFU		
Analytical			
Method(s):	For each variable, summaries (1) and (2) will be provided by treatment group.		
	For applicable variables, summary (3) will be provided by treatment group.		
	(1) Summary of Vital Signs and Weight Parameters and Change from		

50

Baseline by Visit

Descriptive statistics for observed values and changes from baseline will be provided for each visit.

- (2) Case PlotsPlots over time for each subject will be presented.
- (3) Number and Percentage of Subjects with Markedly Abnormal Values of Vital Signs Parameters

Overall frequency distributions of MAV will be provided. If a vital sign parameter has both lower and upper MAV criteria, analysis will be performed for each. Further details are given in Appendix.

5.3.2.2 12-lead ECG

Analysis Set:	Safety Analysis Set		
Analysis			
Variable(s) :	Heart Rate (bpm)		
	RR Interval (msec)		
	PR Interval (msec)		
	QRS Interval (msec)		
	QT Interval (msec)		
	QTcF Interval (msec)	observed value: [Min<= - <=449, 450<= - <=479,	
		480<= - <=499, 500<= - <=Max]	
		change from baseline :	
		[Min<= - <=29, 30<= - <=59, 60<= - <=Max]	
	QTcB Interval (msec)	observed value: [Min<= - <=449, 450<= - <=479,	
		480<= - <=499, 500<= - <=Max]	
		change from baseline :	
		[Min<= - <=29, 30<= - <=59, 60<= - <=Max]	
	12-Lead ECG		
	Interpretation	[Within Normal Limits, Abnormal but not	
		Clinically Significant, Abnormal and Clinically	
		Significant]	
Visit:	(1), (2), and (4): Baseline	e, D14, D28, SFU	
Analytical			
Method(s) :	For each variable other than 12-lead ECG interpretations, summaries (1) and		
	(2) will be provided by treatment group.		
	For applicable variables, summary (3) will be provided by treatment group.		
	For 12-lead ECG interpre-	etation, summary (4) will be provided by treatment	

group.

- (1) Summary of ECG Parameters and Change from Baseline by Visit Descriptive statistics for observed values and changes from baseline will be provided for each visit. Frequency distributions for the categorical variables will be provided for each visit.
- (2) Case PlotsPlots over time for each subject will be presented.

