Appendix 2. Criteria for Markedly Abnormal Values and Elevated Liver Enzyme

(1) Criteria for Markedly Abnormal Values

1) Vital Signs, and 12-lead ECG (except Upper MAV Criteria of QTcF Interval)

For each parameter, all evaluable data (i.e., non-missing and acceptable according to the Handling Rules for Analysis Data) obtained after baseline will be classified as a MAV or not. The criteria in the table below will be used. The lower limit of the normal range and the upper limit of the normal range are abbreviated as LLN and ULN.

Vital Signs

			MAV Criteria	
Parameter	Gender	ender Age	Lower Criteria	Upper Criteria
Systolic Blood Pressure (mmHg)	-	-	<85	>180
Diastolic Blood Pressure (mmHg)	-	-	<50	>110
Pulse (bpm)	-	-	<50	>120
Body Temperature (°C)	-	-	<35.6	>37.7

12-lead ECG

D			MAV Criteria	
Parameter	Gender Age	Lower Criteria	Upper Criteria	
Heart Rate (bpm)	-	-	<50	>120
QT Interval (msec)	-	-	<=50	>=460
QTcF Interval (msec)	-	-	<=50	_

Classifying Subjects for the Overall Treatment Period

For each parameter and subject, classifications will be made according to the conditions i) to iii) provided below. The lower and the upper criteria will be considered separately.

- i) A subject with at least one evaluable data after baseline that meets the MAV criteria will be classified as a subject with MAV.
- ii) A subject who does not meet condition i) and has at least one evaluable data after baseline that doesn't meet the MAV criteria will be considered as a subject without MAV.
- iii) A subject who does not meet conditions i) or ii) will be excluded from the analysis of MAV for that parameter.

2) 12-lead ECG (Upper MAV Criteria of QTcF Interval)

All evaluable data (i.e., non-missing and acceptable according to the Handling Rules for Analysis Data) obtained after baseline will be classified as a MAV or not. The criteria in the table below will be used. Note that the observed value and the change from baseline used for classification should be measurements taken on the same day.

		ender Age	MAV Criteria		
Parameter	Gender		Lower Criteria	Upper Criteria	
QTcF Interval (msec)	-	-	-	If either of the following conditions is met: - observed value >=500 - change from baseline >= 30 and observed value >=450	

Classifying Subjects for the Overall Treatment Period

For each subject, classifications will be made according to the conditions i) to iii) provided below.

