- i) A subject with at least one evaluable data after baseline that meets the MAV criteria will be classified as a subject with MAV.
- ii) A subject who does not meet condition i) and has at least one evaluable data after baseline that meets any of the following will be considered as a subject without MAV.
 - Observed value is less than 450 msec and not missing.
 - Change from baseline is less than 30 msec and not missing, and observed value is less than 500 msec and not missing.
- iii) A subject who does not meet conditions i) or ii) will be excluded from the analysis of MAV.

(2) Criteria for Elevated Liver Enzyme

All evaluable data (i.e., non-missing and acceptable according to the Handling Rules for Analysis Data) obtained after baseline will be used to determine whether each criteria for elevated liver enzyme in the table below is met or not. If there is more than one parameter that need to be considered for a criteria, parameter measurements taken on the same day will be used. The following abbreviations are used: LLN for lower limit of the normal range, ULN for upper limit of the normal range, ALT for alanine aminotransferase, AST for aspartate aminotransferase, Tbili for total bilirubin, and ALP for alkaline phosphatase.

	Criteria for Elevated Liver Enzyme			
Label	(a) Elevated	(b) Not Elevated		
ALT > 3xULN	ALT is greater than 3 times the ULN	ALT is non-missing and less than or equal to 3 times the ULN		
ALT > 5xULN	ALT is greater than 5 times the ULN	ALT is non-missing and less than or equal to 5 times the ULN		
ALT > 8xULN	ALT is greater than 8 times the ULN	ALT is non-missing and less than or equal to 8 times the ULN		
ALT > 3xULN with Tbili > 2xULN	ALT is greater than 3 times the ULN and the total bilirubin is greater than twice the ULN	Either ALT is non-missing and less than or equal to 3 times the ULN, or the total bilirubin is non-missing and less than or equal to twice the ULN		
AST > 3xULN	AST is greater than 3 times the ULN	AST is non-missing and less than or equal to 3 times the ULN		
AST > 5xULN	AST is greater than 5 times the ULN	AST is non-missing and less than or equal to 5 times the ULN		
AST > 8xULN	AST is greater than 8 times the ULN	AST is non-missing and less than or equal to 8 times the ULN		

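### The SAP's overall subject-level QTcF count has no limb for a large change alone, so a rise of more than 60 msec that stays below 450 msec is tabulated as not markedly abnormal

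*SAP*

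**What the plan says.** SAP Appendix 2, part (1) 2), defines the upper MAV for QTcF. A post-baseline reading qualifies if "observed value >=500", or if "change from baseline >= 30 and observed value >=450", with both quantities from the same day. All evaluable post-baseline readings are used. One qualifying reading makes the subject a subject with MAV. Otherwise condition ii) makes him a subject without MAV if he has one reading that satisfies either of two descriptions. The first is "Observed value is less than 450 msec and not missing", with no condition on the change.

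SAP 5.3.2.2 (Part A) and 6.3.2.2 (Part B) also give by-visit frequencies of QTcF change in the categories "Min<= - <=29, 30<= - <=59, 60<= - <=Max", by-visit descriptive statistics, and case plots. All three are tied to listed visits.

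Protocol 6.1.2.1 lists two QT/QTcF findings in the DLT definition: a value above 500 msec, or "QT/QTcF interval prolongation" of more than 60 msec after dosing, with no minimum absolute value. The finding must meet "Either of the following ECG findings at 2 time points 7 or more days apart", and the opening sentence adds that "DLTs are defined as treatment-related AEs that occur within the first 28 days of treatment".

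Protocol 7.2 excludes "QTcF interval > 450 msec" at screening and sets no lower limit.

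**The concern.** 12-lead ECG is a primary endpoint in both Parts, and protocol 4.1.2.5 reports mean QTc rises of about 15 to 20 msec in the earlier study in healthy men. The overall MAV table is the planned output that answers, per subject and over all evaluable ECGs, whether QTcF was ever markedly abnormal. It treats a rise of 30 msec as notable once the value reaches 450, but ignores a rise of any size below 450. The SAP's own by-visit categories and the protocol's DLT definition both single out about 60 msec without a floor on the absolute value. The overall table could therefore read zero although a man had risen by more than 60 msec.

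**Working it through.** **Where the gap lies.** Write b for baseline and o for the observed value. A reading is missed if o − b > 60 and o < 450. Both can hold only if b < 450 − 60 = 390. From b = 390 upward, any change above 60 puts o above 450 with a change above 30, so the second limb catches it. Every value above 500 is caught by the first limb, so only the change criterion has a gap.

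Applying conditions i) to iii) as written:

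| Baseline (msec) | Observed (msec) | Change (msec) | Class |
|---|---|---|---|
| 370 | 449 | +79 | without MAV |
| 380 | 445 | +65 | without MAV |
| 388 | 449 | +61 | without MAV |
| 389 | 450 | +61 | with MAV |
| 400 | 461 | +61 | with MAV |

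In whole msec, the missed values run from 421 to 449 at baseline 360, and from 441 to 449 at baseline 380. Over integer baselines 320 to 450 and observed values up to 560, the highest baseline affected is 388. Adding a limb for change above 60 leaves no missed case on that grid.

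**Whether another table gives the any-time count.** The by-visit tables and case plots use one ECG per window, the one closest to the scheduled day (SAP, Definition of Visit Window). In Part B the WK5D1 ECG window is Days 22 to 98, scheduled Day 29, and WK25D1 is Days 99 to 252. Take a man with baseline 375, a scheduled ECG on Day 29, and a withdrawal ECG on Day 60 showing 440 (+65). The distances from schedule are 0 and 31 days, so the Day 60 reading drops out of the by-visit table and the plot. The MAV table does use it, but 440 is below 450, so it does not count. Even when every crossing is at a selected visit, counts at the seven post-baseline Part B visits cannot be added to give the number of men who ever crossed.

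**Size.** The documents give no QTcF baseline distribution and no SDs. Assumptions, for illustration only:
- Baseline is normal with SD 20, truncated at 450, mean 390, 400 or 410.
- The individual change is normal with mean 17.5 (midpoint of 15 to 20) and SD s = 15, 20 or 25, independent of baseline.

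With f the baseline density, the chance that one reading is missed is

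P(missed) = ∫ over b < 390 of f(b) × [Φ((450 − b − 17.5)/s) − Φ((60 − 17.5)/s)] db.

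P(cross) is the chance of a change above 60 or a value above 500.

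| Mean baseline | P(cross), s = 15 to 25 | P(missed), s = 15 to 25 | Missed share of crossers |
|---|---|---|---|
| 390 | 0.23% to 4.5% | 0.10% to 1.4% | 41% to 32% |
| 400 | 0.24% to 4.5% | 0.06% to 0.80% | 24% to 18% |
| 410 | 0.25% to 4.5% | 0.03% to 0.37% | 11% to 8% |

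In a group of 15, the expected number of missed men per visit runs from 15 × 0.00027 = 0.004 to 15 × 0.01446 = 0.22. One man is 1/15 = 6.7% of a Part B group, or one third of a three-man Part A cohort.

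**The case against.** The strongest reply is that the MAV table is an additional screen. Protocol 13.1.7 asks for descriptive statistics, changes from baseline and cross tables, and the SAP supplies them. Nothing says the MAV rule must match the DLT rule, and elsewhere it is more sensitive: one reading of 450 with a rise of 30 counts. A large rise would usually be visible: the by-visit tables count subjects in the top change category, the summaries give the maximum change, and the case plots show each man. ECG changes judged clinically significant become AEs, and uncorrected QT of 460 msec or more is a separate MAV.

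Most of this stands, and it limits the point to the any-time count. The displays do not fully replace that count, because they drop ECGs further from schedule. The AE route depends on a judgement of clinical significance. The uncorrected-QT rule helps only at slow heart rates: for QTcF 445, QT reaches 460 when RR = (460/445)^(1/0.33) = 1.106 s, about 54 bpm.

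A reader might go further and infer that a DLT goes uncounted. The documents do not support that. One reading of +65 is not a DLT; it needs two time points at least 7 days apart, treatment-relatedness and the first 28 days of Part A. A Part A event so judged has its own table (SAP 5.1.3). Nor is the missing DLT table in Part B a fault, since the DLT evaluation period belongs to Part A only.

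**Conclusion.** The gap is real and follows from the text alone: in the overall QTcF count, a rise above 60 msec from a baseline below 390 that stays under 450 is recorded as without MAV. It is a modest weakness in a primary-endpoint safety table. It is neither a contradiction of the protocol nor a loss of data, since the readings remain in the database and most would appear in a by-visit table. It matters most in Part B, where ECG windows are wide.

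The event is rare and concerns single subjects. The percentages are illustrative. They rest on assumed distributions, on single unconfirmed readings, and on a mean rise that protocol 4.1.2.5 itself describes as unrelated to drug levels. The large missed shares at a mean baseline of 390 are shares of an uncommon event and should not be quoted alone. The change is worth making because it is cheap.

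**What to change.** In the overall QTcF summary for both Parts, using all evaluable post-baseline ECGs, do one of the following.

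1. Add a third upper-MAV limb in SAP Appendix 2 (1) 2): change from baseline greater than 60 msec. In condition ii), let a value below 450 count towards without MAV only if the change is non-missing and no more than 60 msec.
2. Leave the MAV rule as it is and add a separate row: number and percentage of subjects with a change above 60 msec at any time, among those with at least one non-missing change.

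Either costs about one line of SAP text and one program condition. The reported count may become slightly less favourable. Option 1 has a further effect: subjects with a missing baseline and values below 450, now counted as without MAV, would move to excluded and leave the denominator. That should be rare, because ECGs are scheduled at screening and before the first dose. Option 2 leaves the existing MAV denominator untouched.

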Appendix 3. QOL Scoring Procedures

(1) AMS

AMS subscale scores and total scores will be calculated as follows. If one or more of the scores required for the calculation of a subscale are missing, then that particular subscale and the total score will be treated as missing.

- Psychological subscale: sum of severity points from questions 6, 7, 8, 11, 13
- Somatic subscale: sum of severity points from questions 1, 2, 3, 4, 5, 9, 10
- Sexual subscale: sum of severity points from questions 12, 14, 15, 16, 17
- Total score: sum of severity points from all questions from 1 to 17

Reference: Moore C, Huebler D, Zimmermann T, Heinemann LA, Saad F, Thai DM. The Aging Males' Symptoms scale (AMS) as outcome measure for treatment of androgen deficiency. Eur Urol 2004;46(1):80-7

(2) EORTC QLQ-C30

The Global health status/QoL score and each Functional scales score (physical, role, emotional, cognitive, social) will be calculated as follows. The "range" used in the calculations is the difference between the maximum possible values of the score and the minimum possible value. If more than half of the scores are missing, then the Global health status/QoL score or the Functional scales score will be treated as missing. If at least half of the scores are available, then the scores that are available will be used for the calculation.

- Global health status/QoL score: {[(average of item 29 & 30)-1]/range}*100
- Physical functioning: {1-[(average of item 1 to 5)-1]/range}*100
- Role functioning: {1-[(average of item 6 & 7)-1]/range}*100
- Emotional functioning: {1-[(average of item 21 to 24)-1]/range}*100
- Cognitive functioning: {1-[(average of item 20 & 25)-1]/range}*100
- Social functioning: {1-[(average of item 26 & 27)-1]/range}*100

Reference: Fayers PM, Aaronson NK, Bjordal K, Groenvold M, Curran D, Bottomley A, on behalf of the EORTC Quality of Life Group. *The EORTC QLQ-C30 Scoring Manual (3rd edition)*. Published by: European Organisation for Research and Treatment of Cancer, Brussels 2001.

(3) EPIC

Each of the HRQOL Domain Summary Scores (urinary, bowel, sexual, hormonal) will be calculated according to the following steps.

1) Convert score using the conversion table below.

Conversion Table Converted					
Question No.	Answer	Score			
1, 2, 3, 8, 9, 14, 20, 21, 22, 23, 26, 27, 28, 29, 32	1	0			
	2	25			
	3	50			
	4	75			
	5	100			
4	1	0			
	2	33			
	3	67			
	4	100			
5	0	100			
	1	67			
	2	33			
	3	0			
6A, 6B, 6C, 6D, 6E, 6F, 15A, 15B, 15C, 15D,	0	100			
15E, 15F, 24A, 24B, 24C, 31A, 31B, 31C, 31D,	1	100			
31E, 31F	2	75			
	3	50			
	4	25			
	5	0			
7, 10, 11, 12, 16, 25	1	100			
	2	75			
	3	50			
	4	25			
	5	0			
13	1	100			
	2	50			
	3	0			
17A, 17B, 17C, 19	0	0			
	1	0			
	2	25			
	3	50			
	4	75			
	5	100			
18	0	0			
	1	0			
	2	33			
	3	67			
	4	100			
30	1	0			
	2	50			
	3	100			
	4	50			
	5	0			

Conversion Table

2) Each of the HRQOL Domain Summary Scores (urinary, bowel, sexual, hormonal) will be calculated as follows. If 20% or more of the answers are missing then the summary score will not be calculated.

- Urinary summary score: average of converted scores of question no. 1 to 7
- Bowel summary score: average of converted scores of question no. 8 to 16
- Sexual summary score: average of converted scores of question no. 17 to 25
- Hormonal summary score: average of converted scores of question no. 26 to 31

Reference: Takegami M, Suzukamo Y, iHope International. EPIC. 2002.
